| Study Population: | This study will enroll 36 adult subjects. All intubated patients \geq 18 years old who meet criteria for pneumonia and/or sepsis and ARDS according to consensus criteria ^{3,4} will be potentially eligible for inclusion. Subjects will be recruited from the medical, surgical, and cardiac intensive care units (ICUs) at each center. |
| Phase: | Phase Ib |
| Description of Sites/Facilities Enrolling Participants: | The trial will be conducted at 6 tertiary care medical centers including Weill Cornell Medicine/New York-Presbyterian Hospital, Brigham and Women's Hospital (BWH), Massachusetts General Hospital (MGH), Duke (Duke University Hospital/ Durham Regional Hospital), Washington University, and New York-Presbyterian Brooklyn Methodist Hospital. |
| Description of Study Intervention: | Participants will receive algorithm-specified iCO dose (not to exceed 500 ppm) or medical grade air, to achieve COHb of 6-8% over 90 minutes for three consecutive days. |
| Study Duration: | Enrollment will take place over 27 months followed by 9 months for data analysis and dissemination of study results. |
| Participant Duration: | 6 months |

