9.2 SAMPLE SIZE DETERMINATION

As the primary endpoint of this Phase Ib trial is safety, this sample size of 36 (2:1 CO:placebo) was chosen based on a probability to estimate the mean difference between measured and predicted COHb levels in the CO group within 0.5% with 95% confidence to support the accuracy of the CFK equation.

Our preliminary data from our Phase Ia trial demonstrate that the CFK equation is highly accurate at predicting COHb levels following a 20 minute exposure to 200 ppm iCO ($r=0.916$, $R^2=0.9204$; $p<0.0001$). The mean difference between measured and predicted COHb levels was 0.1467 ± 0.2738 . Using a more conservative estimate of standard deviation (SD)=0.6, we will have >99% probability that 95% confidence intervals around the mean difference between measured and predicted COHb levels will be -0.353% to 0.647%. Our calculation includes an 8% dropout rate.

The goal of the safety evaluation for this study is to identify safety concerns associated with CO administration. The ability of the study to detect administration-related AEs or SAEs can be expressed by the true event rate above which at least one SAE would likely be observed and the true event rate below which no events would likely be observed. Specifically, for the CO arm of the study (n=24), there is a 90% probability of observing at least one AE if the true background rate of that AE is 10% and a 97% probability of observing at least one AE if the true background rate of that AE is 15%. For the placebo arm of the study (n=12), there is an 83% probability of observing at least one AE if the true background rate of that AE is 15% and a 91% probability of observing at least one AE if the true background rate of that AE is 20%. In our Phase Ia trial, there were no administration-related AEs and no SAEs related to study product or procedures.

Probabilities of observing one or more events between the groups are presented in **Table 6** below for a range of possible true AE rates. These calculations provide a more complete picture of the sensitivity of this study design to identify potential safety problems with CO.

Table 6. Probability of observing 1 or more events between the groups for different true AE rates

| CO group | | | Placebo Group | | |
|----------|--------------|-----------------------------|---------------|--------------|-----------------------------|
| n | True AE rate | Power to detect ≥ 1 AE | N | True AE rate | Power to detect ≥ 1 AE |

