9.4.4 ANALYSIS OF EXPLORATORY ENDPOINTS (BIOMARKERS)

We will compare biological outcomes between treatment arms using the Mann-Whitney U or t-test for numerical endpoints and either χ^2 or Fisher’s exact test for categorical outcomes. Lipid mediators (LM) and specialized pro-resolving mediators (SPM) levels will be analyzed using principal component analysis (PCA).

We hypothesize that treatment with iCO will reduce plasma levels of mitochondrial DNA (mtDNA), IL-18, and receptor-interacting serine/threonine-protein kinase 3 (RIPK3). Circulating IL-18, mtDNA, and RIPK3 levels will be log transformed before analysis. Based on our prior work, the SD of the log-IL-18 is approximately 0.7, approximately 1.0 for mtDNA, and approximately 2.0 for RIPK3. With 12 subjects in the placebo arm and 24 in the iCO arm, we will have 80% power to detect a difference in IL-18 levels of 0.834 log, which corresponds to an approximate 2-fold difference in plasma IL-18. We will have 80% power to detect a difference in mtDNA of 1.190 log, which corresponds to an approximate 3-fold difference in the circulating mtDNA copy number between the iCO and placebo groups.

We will also have 80% power to detect a difference in RIPK3 of 2.38 log, which corresponds to an approximate 8-10-fold difference in the circulating RIPK3 levels between the iCO and placebo groups. While the magnitude of the putative CO effect on these 3 biomarkers is unknown, we found a 3-fold difference in IL-18 between sepsis patients with and without ARDS and a 4-fold difference in mtDNA between sepsis/ARDS patients and controls. Similarly, we found a 7-fold difference in median RIP3K levels between patients with organ failure and shock compared with ICU patients without organ failure or shock. Therefore detecting differences of these magnitudes is feasible in this patient population. Based on our preliminary data, we will also have 80% power ($\alpha=0.05$) to detect a difference in a number of LM and SPM including PGD₂, PGE₂, PGF_{2 α} , TXB₂, RvD2, and Mar1 (**Table 8**).

Table 8. Minimal detectable difference at 80% power.

| | Mediator | Standard Deviation | Detectable Difference (pg/mL) |
|----------------------------|-------------------------------------|---------------------------|--------------------------------------|
| Pro-inflammatory LM | LTB ₄ | 17.95 | 21.4 |
| | PGD ₂ | 0.68 | 0.81 |
| | PGE ₂ | 1.68 | 2.00 |
| | PGF _{2α} | 1.15 | 1.37 |
| | TXB ₂ | 12.38 | 14.75 |

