| Pro-resolving SPM | RvD ₂ | 12.18 | 14.5 |
| | Mar1 | 15.29 | 18.2 |
| | RvE1 | 10.54 | 12.55 |

We will assess correlations between biomarkers and clinical and lung physiology outcomes including LIS, SOFA, VFDs, as well as 28 and 60 day hospital mortality. We will use multivariable linear regression as the primary model with LIS as the primary outcome variable. Biomarker levels tend to exhibit right skewedness and large outliers, so data will likely require log transformation. Additional predictor variables (such as demographic variables and comorbidities) will be specified *a priori* and interactions between those variables and biomarkers will be included in the model with adjustment for age and sex as important biological variables. To evaluate the predictive ability of biomarkers for binary outcomes, we will use two methods. We will use c-statistics obtained from a logistic regression model to evaluate the effect of biomarker measurements on increasing the area under the receiver operating characteristic (ROC) curves. In addition, we will test if including measured biomarkers to models including important covariates results in an improvement in the net reclassification index as we have done previously for mtDNA.

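### The c-statistic gain and the NRI test for biomarkers are apparently to be computed in the patients used to fit the models, so both are biased upward; how far the NRI test is inflated depends on choices the plan leaves open.

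*Combined protocol and SAP*

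**What the plan says.** Section 9.4.4 introduces this part of the biomarker analysis with "To evaluate the predictive ability of biomarkers for binary outcomes, we will use two methods". The first method reads "We will use c-statistics obtained from a logistic regression model to evaluate the effect of biomarker measurements", the measure being the increase in area under the ROC curve. The second reads "we will test if including measured biomarkers to models including important covariates results in an improvement in the net reclassification index", and the sentence closes by pointing to the group's own earlier practice for mtDNA. So the NRI is the object of a test, not a descriptive supplement. The binary outcomes named just before are hospital mortality at 28 and 60 days.

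The data available are small. Section 1.1 says "This study will enroll 36 adult subjects", and section 9.2 adds "Our calculation includes an 8% dropout rate". Three markers are singled out in 9.4.4 (mtDNA, IL-18 and RIPK3), and Table 8 lists eight lipid mediators. The covariates are given only in part: "adjustment for age and sex as important biological variables", plus further predictors to be fixed in advance.

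The section does not give the NRI variant (category-free or categorical), risk cut-points, variance formula or significance level. It does not say whether markers enter one at a time or together. It describes no validation cohort, sample split, cross-validation, bootstrap or optimism correction, and no previously fitted model to be carried in.

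**The concern.** When a term is added to a logistic model by maximum likelihood, the fitted risks move towards the outcomes in the data that estimated them, even if the term is noise. The NRI counts such movements: deaths whose fitted risk rises and survivors whose fitted risk falls. Computed in the fitting data, it is therefore centred above zero for a useless marker, while its z-test assumes a centre of zero. The c-statistic gain has the same optimism, so the first method does not protect against the second.

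What is at stake is an exploratory claim that a biomarker adds prognostic information. Sections 10.1.4 and 10.1.11 commit to depositing and sharing the biomarker results, so a spurious gain could be taken up by others.

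**Working it through.** The plan gives no figure for this analysis, so there is none to reproduce. The check is a simulation in which the truth is known: the added markers are pure noise.

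**Inputs from the protocol.** n = 36 (section 1.1). With 8% dropout (section 9.2), 36 × 0.92 = 33.1, so about 33 evaluable. Age and sex are in the base model (9.4.4). Smoking is borrowed from the mortality model in 9.4.3.

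**Assumptions.** The protocol gives no mortality rate; 25-35% is assumed, or 36 × 0.25 = 9 to 36 × 0.35 = 12.6 deaths. Cut-points of 20% and 40% are assumed for a three-category NRI. Markers are entered singly, or three jointly.

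**Formulas.** Let a and b be the proportions of deaths whose fitted risk moves up and down, and c and f the same for survivors.

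- NRI = (a − b) + (f − c)
- z = NRI / √v, with v = (a + b)/n_deaths + (c + f)/n_survivors. A second version subtracts (a − b)² and (c − f)² from the two numerators.
- A significant improvement is z > 1.96, so the nominal rate is 2.5%.

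**Why the level fails.** In the category-free version everyone moves, so a + b = c + f = 1 and v = 1/n_deaths + 1/n_survivors. With 11 deaths among 36, v = 1/11 + 1/25 = 0.131 and √v = 0.362. Significance then needs NRI > 1.96 × 0.362 = 0.71. At 30% mortality, three useless markers gave a mean NRI of 0.587, which is 0.587/0.362 = 1.62 standard errors above zero before any real signal. One useless marker gave 0.290, or 0.80 standard errors.

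**Results with useless markers** (2,000 to 3,000 simulated trials per setting):

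| Quantity | Correct value | One marker | Three jointly |
|---|---|---|---|
| Mean category-free NRI | 0 | about +0.26 to +0.30 | about +0.53 to +0.64 |
| Category-free NRI, z > 1.96 | 2.5% | about 7-11% | about 29-40% |
| Three-category NRI, z > 1.96 | 2.5% | about 2-6% | about 12-18% |
| Gain in c-statistic | 0 | +0.02 to +0.03 | +0.06 to +0.08 |
| Ordinary likelihood-ratio test | 5% | 7-9% | 9-13% |

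The ranges cover both variance formulas for the NRI test. The likelihood-ratio row and the split of the c-statistic gain by number of markers come from runs at n = 36 and mortality of 20-40%. With 2,000 trials, the Monte Carlo standard error of a 32% rate is √(0.32 × 0.68/2000) = 1.0 percentage point.

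**Sensitivity** (n = 36, mortality 20-40%, two to six covariates). The category-free test rejects in 7-20% for one marker and 27-56% for three jointly. If three markers are tested one at a time, at least one is significant in 20-47%. The three-category test rejects in 2-6% and 8-27%.

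**Two controls.** Applied to a new sample of 2,000, the same fitted models give a mean category-free NRI of about 0.02 (one marker) and 0.04 (three), and a c-statistic change of −0.01 to −0.03. So the apparent gain comes from re-using the fitting data. At n = 300 with three useless markers, the category-free NRI test still rejects in 22%, against 5% for the likelihood-ratio test. So sample size alone does not repair it.

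**The case against.** The strongest reply is that the plan does not say which NRI it means. A reader might infer that the test is often significant for any useless marker. That holds mainly for the category-free NRI with several markers. With three categories and one marker the rate is about 2-6%, which is little or no inflation. With one marker and the category-free NRI, part of the excess is ordinary small-sample behaviour of logistic regression, since the likelihood-ratio test in the same data also exceeds its level. Nor does the protocol say that mtDNA, IL-18 and RIPK3 will be entered together. This stands, and it is why the size is given as a range.

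Second, use of the same patients is inferred from silence. The sentence refers to earlier work on mtDNA, and the reference list includes a study of circulating mtDNA as a mortality marker whose title mentions derivation and validation. That study may have validated its model, but section 9.4.4 brings in no external data or frozen model for this trial, so the inference remains the natural reading.

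Third, a reader might infer that the plan would report predictive improvement for markers that have none, or that the protocol asserts that all these markers predict mortality. Neither is supported. The first turns an error rate into a certainty. On the second, the hypothesis in 9.4.4 is that iCO lowers plasma levels; section 2.1 cites a mortality correlation for mtDNA only, and prediction is something to be evaluated.

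Finally, the endpoints are exploratory, the main biomarker model is a linear regression on LIS, and no decision is attached to the NRI. That limits the consequence but does not make a miscalibrated test informative.

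**Conclusion.** The concern holds in this form: as written, the c-statistic gain and the NRI would apparently be computed in the 33 to 36 patients used for fitting, and both are then biased upward for useless markers. The upward bias appeared in every setting run. The false-positive rate of the NRI test is less settled: from about nominal (one marker, three categories) to more than ten times nominal (three markers jointly, category-free; 29/2.5 = 11.6). The missing specification is part of the defect, because the variant could be chosen after the results are seen.

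The sizes rest on assumed mortality, cut-points and base covariates, none of which the protocol fixes for this analysis. The primary safety and accuracy endpoints are unaffected. The change is worth making but not critical.

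**What to change.** Amend section 9.4.4 as follows.

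1. Do not test the NRI. Test added value with a permutation or penalised likelihood-ratio test of the biomarker term(s), stating whether markers enter singly or jointly. The ordinary likelihood-ratio test is not enough, since it runs at about 7-13% here.
2. Report the change in c-statistic with bootstrap optimism correction and a confidence interval.
3. If an NRI is shown, give it descriptively, with the variant and any cut-points named in advance and no p-value.
4. Label the results hypothesis-generating.

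The cost is a few sentences and slightly more analysis work. The reported gains will look smaller. No new patients, samples or procedures are needed.

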9.4.5 SAFETY ANALYSES

The primary endpoint is safety of iCO, defined by the incidence of pre-specified administration-related AEs and SAEs. Administration-related SAEs are: 1) myocardial infarction; 2) stroke; 3) new onset arrhythmia requiring DC cardioversion; 4) worsening hypoxemia^{1,2}; 5) COHb \geq 10%; and 6) increase in lactate by \geq 2 mmol/L. The primary endpoint is also accuracy of the CFK equation-based personalized iCO dosing algorithm to achieve a COHb level of 6-8%.

We will examine all AEs including pre-specified administration-related AEs by the type of event, as well as by body system class, and will report proportions and 95% CI. We will compare the occurrence of specific AEs in each arm by the χ^2 test, and the number of AEs per patient in each arm by the Wilcoxon-Mann-Whitney test.

For AEs not included in the protocol defined grading system, the CTCAE Version 5.0 guidelines will be used to describe severity. The CTCAE term, start and stop date, severity, relationship, expectedness, and outcome will be reported for all AEs. A separate table will report the incidence of pre-specified administration-related AEs per arm.

COHb levels will be summarized descriptively reporting mean, standard deviation, median, minimum, and maximum at each time point, each day, by treatment arm. The mean difference between predicted and measured COHb levels with 95% confidence intervals will be presented for the iCO group. Repeated measures analysis of variance (ANOVA) will be used to assess the effects of treatment, time (over 3 days), and the interaction between time and treatment for 90-minute COHb levels. ANOVA will be repeated to assess the effects of treatment, time (over 3 days), entry criteria (ARDS/Sepsis vs. Non-ARDS/Sepsis Pneumonia vs. Non-ARDS/non-Sepsis Pneumonia), and two-way/three-way interactions of time, treatment and entry criteria. We will also compare the occurrence of COHb $\geq 10\%$ in each arm by the χ^2 test.

Accuracy of the CFK equation-based personalized iCO dosing algorithm to achieve target COHb levels will also be analyzed by Spearman correlation and Bland-Altman plots using measured vs. predicted COHb levels and modeled using linear or non-linear regression.

9.4.6 PLANNED INTERIM ANALYSES

Safety monitoring will be conducted on a regular basis by the EC and DSMB. The EC will independently review the safety data in a blinded fashion at regular intervals and make recommendations to the DSMB and NHLBI. The DSMB will meet at least semiannually or after enrollment of 12 subjects, whichever is sooner, to assess safety data on each arm of the study in an unblinded fashion. In addition, all related SAEs will be reported to the DSMB in an expedited fashion and the DSMB would have the option after every SAE report to request an *ad hoc* meeting if safety concerns arise. At this *ad hoc* meeting, the CCC would update the tabulations of all AEs and administration related adverse reactions for Board review. Recommendations by the EC and/or DSMB to amend the protocol or add additional subjects will be reviewed by the sIRB prior to implementation. The EC and/or DSMB may halt enrollment in the study at any time during the trial.

10 SUPPORTING DOCUMENTATION AND OPERATIONAL CONSIDERATIONS

10.1 REGULATORY, ETHICAL, AND STUDY OVERSIGHT CONSIDERATIONS

10.1.1 INFORMED CONSENT PROCESS

10.1.1.1 CONSENT/ASSENT AND OTHER INFORMATIONAL DOCUMENTS PROVIDED TO PARTICIPANTS

Federal regulations 45 CFR 46.111(a)(5) require that informed consent will be sought from each prospective subject or the subject's legally authorized representative (LAR). Consent forms describing in detail the study intervention, study procedures, and risks are given to the participant/LAR and written documentation of informed consent is required prior to starting intervention/administering study intervention.

The investigator is responsible for ensuring that the patient/LAR understands the risks and benefits of participating in the study, and answering any questions the patient/LAR may have throughout the study and sharing any new information in a timely manner that may be relevant to the patient's willingness to continue his or her participation in the trial. All study participants or their surrogates will be informed of the objectives of the study and the potential risks. The informed consent document will be used to explain the risks and benefits of study participation to the patient in simple terms before the patient is entered into the study, and to document that the patient is satisfied with his or her understanding of the risks and benefits of participating in the study and desires to participate in the study. The investigator is responsible for ensuring that informed consent is given by each patient or legal representative. This includes obtaining the appropriate signatures and dates on the informed consent document prior to the performance of any protocol procedures and prior to the administration of study agent.

10.1.1.2 CONSENT PROCEDURES AND DOCUMENTATION

A licensed physician investigator will obtain written informed consent after a detailed review of the consent form with the patient, or more likely, the LAR of the potential study participant. The majority of the patients approached for participation in this study will have limitations of decision-making abilities due to their critical illness or need for sedating medications. Hence, most patients will not be able to provide informed consent. Accordingly, informed consent will be sought from the potential subject's LAR.

The physician investigator will be responsible for ensuring that the subject or LAR understands the risks and benefits of participating in the study, and answering any questions the subject or LAR may have throughout the study and sharing in a timely manner any new information that may be relevant to the subject's willingness to continue his or her participation in the trial. All study participants or their surrogates will be informed of the objectives of the study and the potential risks.

The informed consent document will be used to explain the risks and benefits of study participation to the patient or LAR in simple terms before the patient is entered into the study, and to document that the patient or LAR is satisfied with his or her understanding of the risks and benefits of participating in the study and desires to participate in the study. The investigator is responsible for ensuring that informed consent is given by each patient or legal representative. This includes obtaining the appropriate signatures and dates on the informed consent document prior to the performance of any protocol procedures and prior to the administration of the study agent.

The subject or LAR will be given ample opportunity to read the consent form and ask questions during the initial consent visit and afterwards prior to the signing of the consent form. The subject or LAR will be allowed to discuss the study with anyone they choose before making a decision. The physician investigator obtaining informed consent will explain to the subject or LAR that questions can be addressed at any point throughout the trial and the PI's contact information will be made available during the consent visit for any questions that arise prior to or throughout the study. The subject or LAR will be given a signed copy of the informed consent form, which will include the site PI contact information and the subject or LAR will be encouraged to call with any questions.

For subjects for whom consent was initially obtained from a surrogate, but who subsequently regain decision-making capacity while in hospital, we will obtain formal consent for continuing participation, inclusive of continuance of data acquisition. The initial consent form signed by the surrogate will reflect that such continuing consent will be obtained when possible.

The following categories of surrogates (listed in general order of preference) may provide written informed consent on behalf of potential subjects incapable of providing informed consent themselves, however the exact order will be dependent on the sIRB and local IRB requirements at each site when relying on an sIRB.

- court appointed guardian with specific authority to consent to participation in research or authority to make health care decisions for a class of diagnostic and therapeutic decisions inclusive of the proposed research;
- health care proxy/person with durable power of attorney with specific authority for making health care decisions inclusive of the proposed research; or
- spouse, adult child, or other close family member who knows the subject well and has been involved in their care.

Subjects and/or surrogates will be given a written copy of the consent form, as well as ample time to read and understand the written material. The surrogate will be asked to consider the potential subject's own views prior to providing surrogate consent. An investigator will be available to answer any additional questions. Subjects and/or their surrogates can withdraw consent at any time.

If consent from a LAR or surrogate cannot be obtained in person on behalf of a subject with impaired decision-making capacity, a licensed physician investigator may call the subject's LAR to perform consent by phone according in accordance with the sIRB and each site's IRB policy. Consent obtained by telephone must comply with all regulatory requirements about the process, the consent elements, and documentation of consent.

For subjects for whom consent was initially obtained from a surrogate, but who subsequently regain decision-making capacity while in the hospital, we will obtain formal consent for continuing participation, inclusive of continuance of data acquisition. The initial consent form signed by the surrogate will reflect that such continuing consent will be obtained when possible.

After the patient or his/her legal representative has consented to the study, a copy of the signed informed consent form will also be included in his or her medical record. A note will be included in the medical chart to make other staff aware that the patient was enrolled in the study. The pager number of the PI or Co-investigator will be included in the note to allow the clinical staff to contact the research team at any time.

Remote Consent During COVID-19 Pandemic

Due to infection control measures and hospital visitor policy restrictions during the COVID-19 pandemic, it may not be possible for physician investigators to obtain wet consent from the subject/LAR in person. If unable to obtain wet consent from the subject's LAR in person, the physician investigator will obtain consent remotely via telephone call in accordance with the sIRB and each site's IRB policy and FDA guidance on the conduct of clinical trials during the COVID-19 pandemic. The consent form will be provided to the LAR via secure email or other electronic means including REDCap, Adobe Sign, DocuSign and asked to electronically sign the document, scan or take a picture of the consent signature page, and then return electronically to the research team, in accordance with the sIRB and each relying site's institutional policies.

The physician investigator will electronically sign or print and sign their own copy of the paper consent form and document the consent process in a note to file or informed consent process checklist. Documentation will include that the consent form was provided to the LAR, consent was obtained, the

method used to obtain consent, that the LAR signed a separate copy of the consent form, and the date/time of consent. A compiled copy of the consent including the document with the physician investigator's signature and the LAR's signature consent document will be retained in the study record and a copy of the compiled consent form will be uploaded to subject's medical record. Consent obtained electronically must comply with all regulatory requirements about the process, the consent elements, and documentation of consent.

